#### 7.2 Rationale

In light of the limited data available on use of Repatha® in association with pregnancy and/or lactation, this study is being conducted in response to a request by the EMA to

provide data on outcomes of pregnancy in women (and their infants to the age of 12 months) exposed to Repatha® prior to or during pregnancy and/or breast-feeding.

In women of child-bearing age in Europe, South Africa and Australia those most likely to have been identified as requiring Repatha® for control of hypercholesterolaemia are those diagnosed with FH. Introduction of this particular pharmacological intervention in the majority of non-FH women is anticipated to occur beyond reproductive age.

Considering the low rate of FH diagnosis and the small number of Repatha®-exposed pregnancies anticipated to occur, routine pharmacovigilance surveillance based solely on spontaneous reporting is unlikely to provide the information required by the EMA, in the post-launch period. To address this, a separate study is required, with a targeted, proactive approach to identify cases and seek appropriate follow-up of outcomes of pregnancy in women with FH who have received Repatha® during pregnancy and/or breast-feeding.

This multinational observational study is expected to enrol female FH patients, identified in collaboration with specialist physicians and patient groups:

- Females with FH exposed to Repatha® during pregnancy and/or breast-feeding will form the exposed cohort, and
- Females with FH unexposed to Repatha® during pregnancy and breast-feeding will form the internal comparator group. Although no formal comparison of exposed/unexposed subjects is planned, capturing outcomes of pregnancy in a rare population unexposed to Repatha® will provide contemporary reference **data** against which to consider outcomes in exposed pregnancies.

#### 7.3 Statistical Inference (Estimation or Hypothesis)

No formal hypothesis will be tested in this study. Statistical analyses will be descriptive only. No statistical inference is planned.

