#### 9.5 Study Size

The study will collect data on all pregnancies and births in females diagnosed with FH and identified via the specialist centres/networks, where the patient consents to participate. Based on a conservative estimated FH prevalence of 1 in 500, and a national diagnosis rate varying between 70% and 1% (Nordestgaard 2013), the number of subjects identified for inclusion in this study is not expected to be large. The EMA guideline EMEA/CHMP/203927/2005 "GUIDELINE ON RISK ASSESSMENT OF MEDICINAL PRODUCTS ON HUMAN REPRODUCTION AND LACTATION: FROM DATA TO LABELLING" assumes an overall incidence of birth defects of 3% in order to derive the number of first trimester pregnancies exposed to a medicinal product that is needed to exclude a certain level of risk. The Guideline further states that if no increased incidence of malformations is observed within at least 300 first trimester-exposed, prospectively collected pregnancies with known pregnancy outcomes (births or fetopathological examinations) then the conclusion might be reached that the medicinal product is not responsible for a 10-fold or more increase of the overall incidence of malformations. In accordance with the Guideline, this study will endeavour to enrol 300 pregnancies exposed to Repatha in the first trimester in order to meet the primary objective of this study. The maximum number of unexposed pregnancies will be limited to a ratio of 2 unexposed to 1 exposed; ie, the maximum will be 600 unexposed pregnancies. In addition, the maximum of unexposed pregnancies originating from a single country will be limited to the minimum of N = 150 or tenfold the expected proportion of births out of the combined total of live births as reported by the relevant Bureaus of Statistics in the participating countries (Appendix H). For example, the observed number of live births in Norway in 2017

represented 1.5% of the births across all participating countries. Therefore, no more than N = 88 (10 x 1.5% = 15% of 600) unexposed pregnancies will originate from Norway. The observed number of United Kingdom births represents 19.6% of all 2017 live births across all countries; tenfold 19.6% of 600 would exceed the target of 600, therefore the number of unexposed pregnancies from the United Kingdom will be capped at N=150. This will ensure we enrol as many unexposed pregnancies as possible whilst avoiding that unexposed pregnancies will originate from a single country only.

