#### 9.7.2.4 Analysis of the Primary and Secondary Endpoints

Analysis of Primary Objective:

Congenital anomalies will be summarised and descriptive statistics will be presented.

Congenital anomalies will be defined according to ICD10-BPA codes (codes included in Appendix E: EUROCAT Subgroups of Congenital Anomalies).

Analyses of Secondary Objectives:

Secondary objective outcome measures will be summarised and descriptive statistics will be presented.

Due to potentially insufficient data and consequent lack of statistical power, it is unlikely that comparisons between the 2 groups will provide meaningful results, hence, no formal comparison of exposed/unexposed subjects is planned.

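### The study size is justified by a level of risk that can be excluded, but the plan reports only n and %, with no interval by which any level could be excluded

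*Supplement*

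**What the plan says.** Section 9.5 (and the abstract) derives the exposed sample size from an EMA guideline, which it reports as follows: it "assumes an overall incidence of birth defects of 3% in order to derive the number of first trimester pregnancies exposed to a medicinal product". The stated purpose of that number is to rule out a given risk. The guideline's condition is given as "at least 300 first trimester-exposed, prospectively collected pregnancies with known pregnancy outcomes (births or fetopathological examinations". If no increased incidence is seen in these, the conclusion is said to be that "the medicinal product is not responsible for a 10-fold or more increase of the overall incidence of malformations". The protocol adopts the number on that basis: "this study will endeavour to enrol 300 pregnancies exposed to Repatha in the first trimester in order to meet the primary objective". Unexposed pregnancies are capped at 600.

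The analysis sections do not carry this through.

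- Section 7.3, whose heading covers both estimation and hypothesis, states: "Statistical analyses will be descriptive only. No statistical inference is planned".
- Section 9.7.2.1 gives categorical variables a frequency and a percentage.
- Section 9.7.2.4 summarises congenital anomalies descriptively and plans no formal exposed/unexposed comparison, because "it is unlikely that comparisons between the 2 groups will provide meaningful results".
- The Appendix G template has N in the column heads and n (%) in the cells, shown separately for pre-partum and post-partum enrolment.
- Appendix A lists no stand-alone documents, so the plan points to no other place where an interval might be specified.

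**The concern.** Excluding a level of risk means showing that the data are incompatible with a risk that high. That takes an upper confidence limit and a reference value to read it against. Section 9.5 supplies a reference (3%) and a criterion (10-fold), but the plan never produces the limit. The study size and the reported result are therefore disconnected: the number of pregnancies was chosen to support a kind of statement that the planned output does not contain.

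This matters most if accrual falls short, which the protocol regards as likely. Section 9.5 does not expect large numbers, and the ENCePP checklist in Appendix B expects very few exposed cases. A rate of 3% or 4% from a few dozen pregnancies is compatible with risks several times the background, and nothing in the planned tables states that. This is the primary outcome of a safety study requested by the EMA.

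**Working it through.** **Inputs from the documents.** Background 3%, target 300 first-trimester-exposed pregnancies and the 10-fold criterion (all section 9.5). Reported statistics are n and % (sections 7.3, 9.7.2.1, 9.7.2.4 and Appendix G).

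**Assumption.** The plan gives no confidence level. I use the exact (Clopper-Pearson) two-sided 95% interval. For x events in n pregnancies, the upper limit is the 0.975 quantile of a Beta(x+1, n−x) distribution. For x = 0 this reduces to 1 − 0.025^(1/n). The fold figure is the upper limit divided by 3%.

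**Step 1: can 300 be reproduced from 3% and 10-fold?** The protocol shows no calculation of its own. Ten times 3% is 30%.

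- Zero events: 0/10 gives 1 − 0.025^(1/10) = 30.8%, and 0/11 gives 1 − 0.025^(1/11) = 28.5%. So 11 event-free pregnancies put the limit below 30%. With a one-sided 95% limit, 9 do (28.3%).
- One event: 1/17 gives 28.7% (two-sided), and 1/14 gives 29.7% (one-sided).

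The number needed is 9 to 17 across these conventions, so 300 does not follow from these two figures. With 300 pregnancies, the two-sided limit stays below 30% for as many as 74 events (29.95%). Thus 300 do meet the 10-fold criterion, with a very wide margin.

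**Step 2: what 300 pregnancies give.** Expected events at 3%: 300 × 0.03 = 9. The exact 95% interval for 9/300 is 1.4% to 5.6%. The upper limit of 5.62% is 5.62/3 = 1.87-fold. A one-sided 95% limit is 5.18%, or 1.73-fold.

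This is conditional on the count. If the true rate is 3%, the chance of 9 or fewer events in 300 is 59%. Ten events give an upper limit of 6.0% (2.0-fold), and 14 give 7.7% (2.6-fold). At a true 3%, the chance that the limit falls below 2.5-fold is 93%, and below 3-fold 99.5%.

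**Step 3: what fewer pregnancies give.**

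| Events / pregnancies | Observed | Exact 95% upper limit | Multiple of 3% |
|---|---|---|---|
| 9/300 | 3% | 5.6% | 1.9 |
| 3/100 | 3% | 8.5% | 2.8 |
| 1/50 | 2% | 10.6% | 3.5 |
| 1/25 | 4% | 20.4% | 6.8 |

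Observed rates between 2% and 4% carry upper limits from 5.6% to 20.4%, depending on the number of pregnancies. The percentage alone does not show this.

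**The case against.** The study is openly descriptive. The primary objective is to describe, the checklist calls it signal detection without power, and the same position is taken throughout. Appendix G shows numerators and denominators, so a reader could compute an interval and would not mistake a percentage from 20 pregnancies for one from 300. All of this stands. It makes the gap smaller but does not close it: an exact interval is a descriptive estimate, and a conclusion that the study size was chosen to support should not be left for readers to derive.

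Three stronger readings are tempting, and the documents do not support them.

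- *That the 10-fold statement is wrong, or that 300 fail to deliver it.* They deliver it with room to spare (step 1). Setting 11 pregnancies against a 1.9-fold limit also mixes conditions, since the first assumes zero events and the second the expected nine. On like terms, 0/300 has an upper limit of 1.2%, and 1/11 has 41%. The protocol attributes both 300 and 10-fold to the guideline, whose text is not available here.
- *That citing low power contradicts a target of 300 against 600.* The 600 is a ceiling, the 300 is something the study will endeavour to reach, and numbers are expected to be modest. Section 9.7.2.4 speaks of potentially insufficient data, which fits.
- *That the plan forbids any comparison, so a risk ratio is needed.* Only a formal comparison is excluded. The unexposed cohort is kept as reference data and shown alongside. A risk ratio would be unadjusted, because no covariate assessment or control of confounding is planned, and an interval excluding 1 would be read as a test.

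**Conclusion.** The concern holds in a limited form. The size is justified by excluding risk against a 3% background, while the planned output has no measure of precision, so the report as planned could not state which level of risk it excludes. Describing rather than testing is not a fault in itself; the fault is the mismatch with section 9.5.

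If 300 evaluable pregnancies yield the expected 9 anomalies, the exact 95% upper limit is 5.6%, about 1.9 times the background. This is an expected result, not a guarantee: at a true 3%, a limit that low or lower is reached about 59% of the time. It rests on a two-sided 95% level and on 300 prospective pregnancies with known outcome, whereas the study undertakes only to try to enrol 300 exposed pregnancies and also admits retrospectively identified ones. The 10-fold wording understates what 300 would show; whether it reflects the guideline accurately has to be checked at the source. The change should be made, but the design does not depend on it.

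**What to change.** In sections 7.3, 9.7.2.1 and 9.7.2.4, add estimation without hypothesis testing. Report an exact (Clopper-Pearson) 95% confidence interval for the proportion with a congenital anomaly in prospectively enrolled, first-trimester-exposed pregnancies with known outcome, and the same for the unexposed pregnancies shown alongside. Read the exposed upper limit against the 3% reference. Add the intervals to the Appendix G template. No risk ratio is needed.

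In section 9.5, state the expected precision as conditional figures: an upper limit of about 5.6% (1.9-fold) if 9/300 are observed, 8.5% (2.8-fold) with 3/100, 10.6% (3.5-fold) with 1/50 and 20.4% (6.8-fold) with 1/25. Do not word these as limits that a given number of pregnancies will exclude. Check the 10-fold statement against the cited guideline, and note that on a 3% base it means 30%.

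The cost is some added table content and a few sentences, with no new data collection. The downside is that wide intervals become visible if enrolment is small.

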#### 8. Research Question and Objectives

The purpose of the study is to evaluate outcomes of pregnancy in females diagnosed with FH, exposed to Repatha® during pregnancy. This includes follow-up of their infants to the age of 12 months.

#### 8.1 Primary Objective

To describe congenital anomalies in infants of females with FH exposed to Repatha® within 15 weeks prior to or during pregnancy, followed to the age of 12 months.

#### 8.2 Secondary Objectives

- To describe outcomes of pregnancy (other than congenital anomalies) in females with FH exposed to Repatha® within 15 weeks prior to or during pregnancy
- To describe outcomes of pregnancy in females with FH not exposed to Repatha® within 15 weeks prior to or during pregnancy
- To describe **health and developmental** outcomes in infants up to the age of 12 months, born to females diagnosed with FH and **unexposed or** exposed to Repatha® **during pregnancy and/or breastfeeding.**

#### 9. Research Methods

#### 9.1 Study Design

The study is a multinational (Europe, South Africa and Australia) prospective observational cohort study designed to capture data on outcomes of pregnancy in women diagnosed with FH. Within this population, the exposure of interest is administration of Repatha® during pregnancy and/or breast-feeding. The primary and secondary outcome measures are congenital anomaly and other outcomes of pregnancy **or infancy**, respectively.

To maximise the enrolment of eligible subjects this study will be conducted at sites which specialise in treatment of FH patients, and which are connected to local national and regional FH patient groups. All eligible patients at each study site will be invited to consent to be enrolled into the study; there is no limit to the number of subjects enrolled.

At the individual subject level, data of interest include demographics, medical and obstetric history at the time of confirmation of pregnancy within the study observation period. The subject will be followed **to determine** the outcome of pregnancy, including follow-up of the infant(s) to 12 months post-delivery. Data capture may be retrospective if a pregnancy occurring during the study period is detected after delivery.

Study site staff will abstract data from patient notes and entered into the sponsor's electronic database. There will be independent external expert adjudication of congenital anomaly to ensure consistency and accuracy of reporting. Analyses will be conducted by the sponsor.

This is a non-interventional, observational study and is not intended to alter the clinical management of patients.

#### 9.2 Setting and Study Population

#### 9.2.1 Study Period

Data will be captured for pregnancies occurring between June 2016 and June 2026.

#### 9.2.2 Selection and Number of Sites

Sites in Europe, South Africa and Australia where pregnant FH patients are treated will be considered suitable. These are anticipated to be national or regional FH referral centres, or other specialist sites which treat FH patients. Potential sites will be approached and selection confirmed according to Amgen Standard Operating Procedures (SOPs), based on interest in participation as a study site, willingness and ability to comply with the protocol and data entry conventions, and agreement to follow the subjects throughout the observation period.

**An estimated 50 to** 70 sites are expected to participate in the study. As many countries as possible within Europe, as well as South Africa and Australia, are invited and encouraged to participate. Site identification is expected to continue during the course of the study, to maximise the catchment across the FH population and hence the number of potential study subjects.

To maximise the number of subjects enrolled:

- A key criterion for selection of a study site is that the Investigator is a physician specialising in the treatment of FH.
- The Investigator will be aware of pregnancies in the regional or national FH population and will routinely advise women on management of their FH during pregnancy and breast-feeding.
- The Investigator and the sponsor will seek to proactively engage with national and local FH patient networks, to raise awareness of the study.
- Physicians may also be contacted if Repatha®-exposed pregnancies at their clinic are reported through Amgen's routine surveillance system; patient confidentiality will not be breached; the physician will be alerted to the pregnancy and will be encouraged to consider the patient's eligibility and invite them to consent to enrol in the study.
- There is no limit on the number of sites to be opened; as many sites as possible will be sought, in all participating countries, with no minimum on the number of eligible subjects expected to be enrolled at any site.

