#### 9.9.2 Selection Bias

The intention is to enrol as many eligible subjects as possible, with no limit on numbers at site or country level. The inclusion criteria are not restrictive, and all eligible FH women identified will be invited to enrol into the study.

Selection bias may occur due to pregnant women without adverse outcomes potentially being less likely to be told about the study, or less inclined to participate in the study. To help to minimise selection bias arising from preferential enrolment of subjects experiencing adverse outcomes rather than those with normal outcomes, sites will be requested to enrol all eligible patients whether retrospectively or prospectively identified, and regardless of outcomes which are already known.

To account for the possibility that subjects enrolled retrospectively may differ from those enrolled prospectively, data obtained from retrospective and prospective subject identification will be reported separately.

Study sites will be asked to record, annually for the duration of the study, the number of pregnant FH women attending their clinic, and the number who are eligible but do not consent to enrol into the study. Comparing these numbers with the number of enrolled subjects will help to assess case ascertainment.

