#### 11. Collection of Safety Information and Product Complaints

In this study, Safety reporting is required only for subjects exposed to Repatha®

For subjects known to be exposed to Repatha® within the 15 weeks prior to or during pregnancy and/or during breastfeeding, a Pregnancy Notification Worksheet and/or Lactation Notification Worksheet (Appendix I), as appropriate, is to be submitted to Amgen and will be collected until termination of breastfeeding, otherwise until **12 months post-partum**.

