#### 11.1.3 Other Safety Findings

Other Safety Findings (regardless of association with an adverse event) include:

- Medication errors, overdose, whether accidental or intentional, misuse, or abuse, involving an Amgen product,
- Pregnancy and lactation exposure,
- Transmission of infectious agents,
- Reports of uses outside the terms for authorized use of the product including off-label use,
- Occupational exposure,
- Any lack or loss of intended effect of the product(s).

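### The surveillance-referral route in Section 9.2.2 is open to exposed pregnancies only, and no planned variable or table isolates the pregnancies that enter by it

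*Supplement*

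**What the plan says.** Section 9.2.2 lists ways to maximise enrolment. One applies when "exposed pregnancies at their clinic are reported through Amgen's routine surveillance system": "the physician will be alerted to the pregnancy and will be encouraged to consider the patient's eligibility and invite them to consent". No counterpart is described for women not taking Repatha, and a product surveillance report could not exist for them.

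Sections 9.9.1 and 9.9.2 accept that pregnancies with adverse outcomes may be enrolled preferentially, mainly in connection with retrospective recruitment. They do not mention the surveillance route or that it reaches one cohort only. Section 9.9.2 offers three safeguards:

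- Sites are asked to enrol every eligible woman, whatever outcome is already known.
- "data obtained from retrospective and prospective subject identification will be reported separately". Appendix G carries this out with pre-partum and post-partum enrolment blocks inside each exposure column.
- Sites log each year "the number of pregnant FH women attending their clinic, and the number who are eligible but do not consent to enrol into the study".

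Section 9.3 lists the variables. None states how a pregnancy came to the study's attention. The strata in 9.7.2.7 are timing of exposure, other lipid therapy, and retrospective or prospective identification.

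**The concern.** Selection that acts equally on both cohorts shifts both percentages. Selection that acts on one cohort distorts the contrast between them. The protocol plans no formal comparison, but Section 7.2 still offers the unexposed women as contemporary reference data for the exposed outcomes, and Appendix G prints the columns side by side. Appendix B calls this a signal detection study. With about nine anomalies expected among 300 exposed pregnancies, a handful of selected cases would change the picture.

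The gap lies with referrals enrolled before delivery. Section 9.1 ties retrospective capture to detection after delivery, so the planned split turns on delivery and not on whether an abnormality is already known. A woman reported to the sponsor after an abnormal scan and then enrolled is counted pre-partum, beside clinic-identified women. That block is the closest to the prospectively collected pregnancies on which the target of 300 rests.

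**Working it through.** **Inputs from the documents.** Section 9.5: "this study will endeavour to enrol 300 pregnancies exposed to Repatha in the first trimester"; a background malformation incidence of 3%; at most two unexposed pregnancies per exposed one. The plan's own ceiling reproduces: 2 × 300 = 600. Expected anomalies with no drug effect: 300 × 0.03 = 9.

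**Inputs not in the documents (assumed).** The share *s* of exposed pregnancies that come through surveillance, and the anomaly rate *q* among them. I take *s* from 5% to 30% and *q* from 10% to 30%, with 3% among all others.

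**Step 1: pooled exposed rate with no drug effect.** Rate = (1 − *s*) × 3% + *s* × *q*. For *s* = 10%, which is 30 of 300:

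- *q* = 10%: (270 × 0.03 + 30 × 0.10)/300 = (8.1 + 3)/300 = 3.7%
- *q* = 20%: (270 × 0.03 + 30 × 0.20)/300 = (8.1 + 6)/300 = 4.7%

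The last column gives the binomial chance, at the pooled rate, of 15 or more anomalies in 300. Fifteen is my marker, not the plan's.

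| *s* | *q* | Pooled rate | Ratio to 3% | Expected anomalies | P(15 or more) |
|---|---|---|---|---|---|
| any | 3% (no enrichment) | 3.0% | 1.00 | 9.0 | 3.9% |
| 5% | 10% | 3.35% | 1.12 | 10.1 | 8.3% |
| 10% | 10% | 3.7% | 1.23 | 11.1 | 14.9% |
| 10% | 20% | 4.7% | 1.57 | 14.1 | 44.0% |
| 20% | 20% | 6.4% | 2.13 | 19.2 | 86.9% |
| 30% | 30% | 11.1% | 3.70 | 33.3 | over 99% |

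**Step 2: what Appendix G would show.** Take *s* = 10% and *q* = 20%, and assume also that 80% of the 270 other pregnancies enrol pre-partum (216 pre-partum, 54 post-partum).

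| When the 30 referrals enrol | Pre-partum block | Post-partum block |
|---|---|---|
| All post-partum | 6.48/216 = 3.0% | (1.62 + 6)/84 = 9.1% |
| Half and half | (6.48 + 3)/231 = 4.1% | (1.62 + 3)/69 = 6.7% |
| All pre-partum | (6.48 + 6)/246 = 5.1% | 1.62/54 = 3.0% |

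In the first case the split exposes the excess, although it cannot say which route caused it. In the last case the excess sits in the block a reader would trust most, and nothing in the table marks it.

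**Step 3: the site log.** As described, it gives each site's total of pregnant FH women and of eligible non-consenters. Without a split by exposure, it cannot show whether a larger fraction of exposed than of unexposed pregnancies was enrolled.

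**The case against.** The case against is substantial, and much of it stands.

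- **Planned safeguards.** A reader might infer that no planned table would reveal such enrichment, or that separate reporting is the only control. Neither is so. Reports prompted by a bad outcome will often follow that outcome, and those women fall in the exposed post-partum rows. Section 9.9.2 adds the request to enrol everyone and the log. What remains is narrower: referrals enrolled before delivery, and attribution of any excess.
- **Direction.** A reader might infer that the exposed rate will be biased upward. The documents do not establish that. Section 11.1.3 places exposure in pregnancy under a heading that begins "Other Safety Findings (regardless of association with an adverse event) include", so uneventful pregnancies are reportable too. Section 9.1 already has all eligible patients at a study site invited, so the route may partly recover women who were missed.
- **Missing variable.** Section 9.3 does not list enrolment date or retrospective status either, although the tables need them, and no eCRF or SAP is shown. Absence from 9.3 is therefore weak evidence that source goes uncollected. It remains true that the protocol specifies its strata and table layout and includes none by source.
- **Size.** The shifts to 3.7% and 4.7% lie inside the exact 95% interval for 9 of 300, which is 1.4% to 5.6%. The only benchmark in Section 9.5 is a 10-fold increase, well beyond the 3.7-fold worst case above. At this sample size, selection and drug effect would be hard to separate even without the route.
- **Excluding referrals.** It is tempting to drop referred pregnancies from the main exposed figure. If referrals are enriched, that would preferentially remove exposed anomalies from the headline of a safety study and could bias it downward. It would also shrink a rare cohort.

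**Conclusion.** The point holds as a gap in detecting bias, not as a demonstrated bias. The route exists, only exposed pregnancies can enter by it, 9.9 does not name it, and no planned variable or table isolates it. For referrals enrolled before delivery, a report that follows the protocol could not separate differential selection from a drug effect. Enrichment from reports made after the outcome would largely be visible in Appendix G.

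No size can be derived from the documents. Under the assumption of 30 referrals among 300 with 10% to 20% anomalies, and 3% otherwise, the pooled rate is 3.7% to 4.7%, or 1.2 to 1.6 times background. Smaller or larger shares move it as tabulated, and with no enrichment it stays at 3%. A reading that the exposed percentage is inflated, or that the planned tables are blind to it, goes further than the text allows. The change is a worthwhile and inexpensive improvement.

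**What to change.** 1. Record on the eCRF how each pregnancy was identified: site clinic, patient network, or sponsor surveillance referral. Set a rule for women known to more than one source, for example what first brought the pregnancy to the site's attention for enrolment. The rule should say that the notification worksheet Section 11 requires for exposed subjects does not itself make a woman a referral.
2. Record whether a fetal or infant abnormality was already known at enrolment.
3. Keep all exposed pregnancies in the main summary. In 9.7.2.4 and Appendix G, add rows by source, and show the exposed anomaly and pregnancy-outcome figures with and without surveillance-referred pregnancies as a sensitivity display. Section 9.7.2.5, which now plans none, would need to agree.
4. Split the annual site log in 9.9.2 by Repatha exposure.
5. Name the route in 9.9.2 as one that reaches the exposed cohort only.

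The cost is one or two eCRF fields, some table rows with small counts, and a split of a log that sites already keep. No exposed pregnancy is lost from the main figure. Source may be hard to reconstruct later, so it is best captured at enrolment.
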